K23 Aim 2 Study Protocol

Brown University School of Public Health

PI: [name]

Study Staff:

[name] (RA)

[name] (data manager)

RA TBA

[name] (research consultant)

Mindfulness Teachers:

[name]

[name]

Funded by: US National Institute of Health K23AT011173, "Developing internet-delivered, mindfulness-based intervention to reduce HIV risk and promote mental and sexual health among young adult MSM"

Co-Investigators:

[name]

[name], MD

[name]

[name], MD

[name], MD

Last updated: June 21st, 2022

1. SPECIFIC AIMS (5-year project; Aim 2 highlighted)

In 2017, gay, bisexual, and other men who have sex with men (MSM) made up 70% of new HIV infections in the U.S., and young adult MSM (age 18-34; YMSM) account for the majority of HIV cases. YMSM also experience prevalent, often co-occurring mental health issues, including depression, anxiety, and substance use, creating a “syndemic” condition surrounding HIV risk and suboptimal HIV testing.

A key driver of such disparities experienced by YMSM is minority stress. Experiences of identity-based discrimination lead to internalized stigma and maladaptive coping (e.g., emotion dysregulation, avoidant coping, impulsivity). The “downstream” effects of minority stress are poor mental health (depression and anxiety), increased sexual risk, and lack of engagement in key health services such as HIV testing due to anxiety related to identity disclosure to providers and anticipation of stigmatizing encounters. Recent evidence also suggests discrimination exposure is linked to heightened physiological stress response (cortisol level) that represents depletion of coping resources and increased risk for development of stress-linked psychological disorders (depression, anxiety). Therefore, **reducing minority stress represents a promising transdiagnostic approach to reduce the burden of HIV and mental health issues experienced by YMSM.**

Our research suggests that MBIs target mechanisms relevant to minority stress, including self-acceptance, emotional dysregulation, and avoidant coping. Therefore, as an individual-level intervention, MBIs may serve as an innovative HIV prevention intervention by lowering the syndemic risk among YMSM through reducing psychological symptoms, improving coping, and enhancing HIV-related behavioral health. However, no evidence-based MBIs have been tested for HIV prevention, and clinical and research evidence suggests further adaptation is warranted to improve its relevance and optimize engagement for YMSM.

This K23 aims to develop an internet-delivered MBI to address minority stress and its negative HIV-related health consequences experienced by YMSM. Specifically, we propose to adapt, refine, and pilot-test an evidence-based MBI, Mindfulness-based Stress Reduction (MBSR), to promote mental and sexual health and HIV testing engagement among distressed, high-risk YMSM. Aims 1-3 will support the subsequent production and evaluation of the adapted intervention. To maximize reach, scalability, and availability to a population that experience challenges seeking in-person counseling and health services, the intervention will also be adapted for internet-based delivery.

Aim 1. Adapt MBSR for distressed, high-risk YMSM using internet delivery, guided by the ADAPT-ITT model. We will conduct iterative phases of formative research including online-based focus groups with YMSM, solicitation of feedback from stakeholders, and revision of intervention protocols. This process will result in the first-draft of an internet-delivered, mindfulness-based intervention protocol for use with YMSM.

Aim 2. Refine intervention protocol by administering adapted materials to distressed, high-risk YMSM ($n=18$) through internet-based open pilot and gather feedback. Following integration of feedback, this process will result in a finalized protocol of an internet-delivered, mindfulness-based intervention protocol for YMSM.

Aim 3. Examine the feasibility and acceptability of an internet-delivered mindfulness-based intervention (iMBI) for HIV prevention. A sample of 40 distressed, high-risk YMSM will be randomized into the adapted iMBI or a waitlist control condition. Primary outcomes are HIV testing and self-reported sexual risk behaviors. Secondary outcomes are stress biomarker (hair cortisol), psychological health, minority stress and coping. The study will examine recruitment and retention, number of sessions attended, self-reported at-home practice of mindfulness, completion of assessment, and acceptability of the intervention.

2. Inclusion and Exclusion Criteria (updated Spring 2022):

The following is the most updated inclusion/exclusion criteria, and inclusion of STI testing (beyond HIV self-testing, we are also including STI self-testing, including Chlamydia and Gonorrhea):

- Inclusion criteria:
 - (1) assigned male at birth,
 - (2) being 18 to 34 of age,
 - (3) identify as a cisgender man,
 - (4) reside in the United States,
 - (5) can read and speak English,
 - (6) engaged in condomless anal sex with another man in past 6 months,
 - (7) endorse distress, measured by the PHQ-9 and GAD-7,
 - (8) possess a device (phone, tablet, computer) that allows for online conferencing.
 - (9) HIV-negative or status unknown
- About HIV status: In Aim 2, HIV status will be assessed by self-report only (due to budget and non-intervention activity for these Aims). We will provide rapid oral HIV testing in Aim 3.
- Exclusion criteria: YMSM will be excluded from the study if they are determined to have symptoms that would prevent them from giving meaningful consent or participate in study activities including any of the following criteria:
 - (1) Significant cognitive impairment
 - (2) Psychosis
 - (3) Imminent suicidal risk
 - (4) Substance abuse
- YMSM will be excluded from the study if they are determined to have symptoms preventing them from giving meaningful consent or study activities including (1) significant cognitive impairment, (2) psychosis, (3) imminent suicidal risk, and (4) substance abuse.

3. Steps in Recruitment, Screening, and Assessment:

Recruitment and Screening Procedures

- 1) **Timeline for recruitment:**
 - a. All prep efforts to be ready **6-8 weeks prior** to the open pilot group
 - b. Recruitment efforts to take place **a month prior** to the open pilot group
- 2) Recruitment will be conducted through 6 methods:

 - a. Participants data will be stored on a secure server ([name] SPH folder or stronghold folder)
 - b. During recruitment, study enrollment, and post-intervention assessment, RA will check daily on Qualtrics regarding:
 - i. Number of people screened, potentially eligible participants, who to email, etc.
 - ii. Data flow, any issues to be reported in order to revise recruitment strategy
 - iii. Data quality (e.g., any fraud activities)

11) Participant contacts during the study:

- a. Retention: **Retention** information includes multiple contact details for participant as well as contact information from a trusted friend or relative to serve as an alternative contact. Study RA will use additional recruitment techniques in Aims 2-3 given their longitudinal design. This includes phone reminders, updating of contact information, and calling their alternative contact as needed.

An abbreviated study flowchart is presented.

Online, targeted recruitment

Fenway
FB-groups
University organizations and CBOs
CAB

Online screening for eligibility (10 mins)

Obtain consent online

Contact

Potentially eligible individuals will be directed to contact form
RA will contact and schedule zoom screening

Zoom Screening

RA will conduct camera-on screening to determine eligible and orient participants to the study

Baseline Survey

Participant will use individualized link to complete baseline assessment (40 mins)

Group intervention

Participant will receive the intervention
RA/TA will have a welcome call and mid-term check-in with participants

Post-group assessments

Participant will use individualized link to complete post-intervention survey via Qualtrics (40 minutes)
Participant will complete an exit-interview with researcher (1.5-2 hours)

4. Intervention protocol

- 1) Participants will receive 10-week group-based intervention, including 1 week of orientation and 9 weeks of classes (including a week of retreat)

2) Participants will also receive two check-ins from the Teaching Assistant, including 1-2 weeks since the start of the class (the welcome call), and mid-term check-in (after session 5). TA will use motivational interviewing skills to learn about participants' intention for participation, goals and expectations, experiences in the group so far, potential challenges/barriers, etc.

As suggested by CAB, TA will also function as a channel of communication if participant experience adverse events/reactions during the course of intervention.

3) Teachers will receive ongoing weekly supervision to support their work.
 4) Once the group intervention ends, TA will contact participants about next steps re:
 a) Complete post-group survey
 b) After survey, we will schedule zoom interview with a study team member

5. Baseline and Post-Pilot (2.5 months FU) Qualtrics Assessment:

- 1) At baseline, participants will fill out assessments related to:
 - a. demographics
 - b. primary outcomes (sexual risk behavior only, no testing)
 - c. secondary outcomes
 - d. exploratory outcomes
- 2) During the intervention, participants will complete weekly report on:
 - a. monitoring of sexual risk (condomless sex)
 - b. monitoring of depression (PHQ-9) and anxiety symptoms (GAD-7)
 - c. log on weekly/daily practice (via Qualtrics- individualized links)
 - d. report on attendance (from zoom sessions)
- 3) At post-intervention (2.5 months FU), participants will complete assessments related to:
 - a. Via Qualtrics:
 - i. Primary outcomes
 - ii. Secondary outcomes
 - iii. Exploratory outcomes
 - iv. Acceptability measures
 1. note that this includes description on two methods of cortisol collection (hair or nail) and ask participants to rate their willingness
 - b. Via Zoom-based interview
 - i. Interview will be conducted after completion of all other study activities

Table 1. Measures of Feasibility, Acceptability, and Outcomes		Baseline	During Intervention	Post-Intervention
Demographics	Socio-demographics	X		
Primary outcomes	Sexual risk behaviors	X	X	X
Secondary Outcomes	Depression: PHQ-9 (also monitored weekly)	X	X	X
	Anxiety: GAD-7 (also monitored weekly)	X	X	X

	Internalized Homophobia Scale	X		X
	Difficulties of Emotion Regulation (DERS)	X		X
	Sexual Compulsivity Scale (SCS)	X		X
	Safe Sex Self-Efficacy Scale	X		X
Exploratory Outcomes	PTSD: PCL-5	X		X
	Resilience	X		X
	UCLA Loneliness Scale	X		X
	HIV knowledge	X		X
	PrEP willingness	X		X
Feasibility	Recruitment	X		X
	Attendance & attrition		X	
	Weekly report of home practice - log		X	
Acceptability	Missing data in assessment	X		X
	Session Evaluation Form			X
	Client Satisfaction Survey (CSQ-8)			X
	Questions related to cortisol collection			X
	Exit-interview (Qualitative)			X

7. Post-Pilot (2.5 months FU) Exit-Interview

- 1) RA will schedule exit-interview after participant completes all other study activities
- 2) Exit-interview will focus on participant's experience in the study, feasibility and acceptability of the intervention, areas for further adaptation, etc.
- 3) One-on-one, Zoom-based interview will be conducted by a study team member or PI. Interview will be recorded. The recording will be stored on a secure server.
- 4) Team will transcribe and analyze qualitative data.

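### Minor, cheap improvement: adverse reactions reach the record only if a participant raises them, and neither Table 1 nor the SAP lists a harm summary

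*Protocol*

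**What the plan says.** Participants must "endorse distress, measured by the PHQ-9 and GAD-7" (Protocol section 2, inclusion 7). Imminent suicidal risk excludes a person at entry (exclusion 3).

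Section 4, 2) contains the one sentence on adverse events, which the protocol credits to a CAB suggestion: "TA will also function as a channel of communication if participant experience adverse events/reactions during the course of intervention". The same item schedules two TA check-ins, a welcome call and a mid-term call after session 5. Their topics include "experiences in the group so far, potential challenges/barriers, etc".

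Section 5, 2) sets out a weekly report covering condomless sex, PHQ-9, GAD-7, home practice and attendance, and calls the symptom part monitoring. Table 1 adds pre/post scales, among them PCL-5, DERS, the Sexual Compulsivity Scale and the UCLA Loneliness Scale. It has no row for adverse events.

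The exit interview (section 7, 2) concerns the participant's "experience in the study, feasibility and acceptability of the intervention, areas for further adaptation", and takes place after all other study activities are complete.

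The SAP names five kinds of descriptive summary: recruitment, retention/attrition, attendance, the satisfaction questionnaire and the session evaluation form. It adds a template analysis of the exit interviews.

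**The concern.** An event that has to be volunteered is recorded only if the participant recognises it, links it to the programme and chooses to mention it. A group selected for distress is one in which adverse reactions to an intervention should be asked about directly.

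The purpose of this pilot is to refine the intervention before the randomised Aim 3, and adverse reactions are part of what a refinement pilot should supply. Run as written, the quantitative results would describe satisfaction and attendance and contain no harm count. A reader could not tell an absence of harm from an absence of questions.

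A second, smaller matter is that suicidal risk is screened at entry and the PHQ-9 is then repeated weekly, but the documents do not say who reads the answers or what happens next.

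**Working it through.** The documents give no harm rate or safety-based sample size, so there is no stated figure to reproduce. The check is mainly a comparison of every planned contact and form with one question: is it stated to ask about adverse reactions?

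| Contact or form | Stated content | Adverse reactions named as a question? |
|---|---|---|
| TA channel (section 4, 2) | Available if an event occurs | No; waits for the participant |
| Two TA check-ins (section 4, 2) | Intention, goals, experiences, challenges; open list | No |
| Live classes, weekly teacher supervision (section 4) | Teaching and support for teachers | No |
| Weekly report (section 5, 2) | Condomless sex, PHQ-9, GAD-7, practice, attendance | No |
| Pre/post survey (Table 1) | Outcome scales, satisfaction, session evaluation | No row; the evaluation form's content is not shown |
| Exit interview (section 7) | Experience, feasibility, acceptability, adaptation; open list | No |
| SAP summaries | Five feasibility and acceptability measures | No |

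Two details bear on completeness. No TA check-in is scheduled after session 5, although classes continue and the TA channel stays open throughout. The exit interview follows completion of everything else, so people who stop early may not reach it.

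**What a harm table could say.** Input: n = 18 (Protocol section 1, Aim 2). Exact (Clopper-Pearson) 95% limits:

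- 0 events: upper limit 1 − 0.025^(1/18) = 0.185, so 0% to 18.5%.
- 1 event: 1/18 = 5.6%, limits 0.1% to 27.3%.
- 2 events: 2/18 = 11.1%, limits 1.4% to 34.7%.

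**Why asking matters at this size (illustration only).** Let p be the share of participants with a harm the planned measures do not pick up, and c the share of those harms that gets recorded. Both are assumptions. The chance that the pilot records at least one is 1 − (1 − p·c)^18:

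| Assumed p | c = 100% | c = 50% | c = 25% |
|---|---|---|---|
| 5% | 0.60 | 0.37 | 0.20 |
| 10% | 0.85 | 0.60 | 0.37 |
| 20% | 0.98 | 0.85 | 0.60 |

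For example, at p = 10% and c = 50%, 1 − 0.95^18 = 0.60, against 1 − 0.90^18 = 0.85 with full capture. The documents do not say what c would be.

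**The case against.** The strongest reply is that this pilot has many ways of noticing harm. Participants meet live each week, teachers are supervised weekly, and the TA calls twice with open questions and remains reachable. Mood and anxiety are scored weekly, condomless sex is reported weekly, and trauma symptoms, emotion regulation, sexual compulsivity and loneliness are measured before and after. A long exit interview is analysed by template. Several lists are open-ended, and a separate safety plan may exist outside these pages. Much of this stands. It makes wholesale missing of harms unlikely, and it is why the point is minor. None of it supplies a standard question or a count.

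Three stronger readings are tempting and should be resisted.

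- A reader might infer that nobody looks at the weekly scores, because section 3, 10) b says "During recruitment, study enrollment, and post-intervention assessment, RA will check daily on Qualtrics regarding" and does not name the intervention weeks. That clause sits under recruitment and screening and concerns counts, data flow and fraud, so its silence is not evidence about safety review. The fair statement is that the protocol calls the scores monitored and names no reader or action.
- A reader might infer that every harm outside PHQ-9, GAD-7 and PCL-5 goes unmeasured. The other scales, the condomless-sex reports and the attendance records contradict that.
- A reader might want the SAP faulted for having no analysis of symptom worsening, or a referral rule based on score rises. The SAP specifies no analysis of any outcome scale, so that is a broader matter. A score-rise rule would need a cut-off that the documents give no basis for choosing.

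**Conclusion.** The point holds as a minor, inexpensive improvement. The stated adverse-event route is passive, no contact or form is stated to ask about reactions, Table 1 has no adverse-event row, and the SAP lists no harm summary. The consequence is that some harms may be under-captured and that none is planned to be tabulated. The documents do not show that harms will be missed.

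The extent of under-capture cannot be computed. The n = 18 intervals are exact for the planned sample and assume that every participant is asked. They would be wider with fewer. Even a clean result would leave rates up to 18.5% open, so the table is useful for refining the intervention and cannot establish safety. The conclusion also assumes that no separate safety plan already covers this. If one does, a cross-reference and the SAP lines would be enough.

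**What to change.** 1. Add one standard adverse-reaction item to the weekly Qualtrics report, the two TA check-ins and the post-intervention survey. For those who stop attending, use the retention contacts already planned in section 3, 11) ("phone reminders, updating of contact information, and calling their alternative contact as needed"), putting the question to the participant and not to the alternative contact. Add an adverse-event row to Table 1, during and after the intervention.
2. Name an existing staff member to read each weekly report on receipt and refer any positive PHQ-9 suicidality item to the investigator.
3. In the SAP, report n (%) of participants with any adverse event and with any serious adverse event, each with an exact 95% interval, descriptively.

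**Cost.** One item in two surveys and two calls, one table row, a short SAP addition, and up to 18 reports to read a week if all participants are in one group. The documents give no rate for positive suicidality items. If 2% to 20% of forms were positive (an assumption), referrals would run at 18 × 0.02 = 0.4 to 18 × 0.20 = 3.6 a week. The downside is that direct questioning records more minor events, which is why serious events get their own line. No extra visit, staff or participants are needed.

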**Mindfulness-based Queer Resilience (MBQR) to Promote Mental and Sexual Health among Sexual and Gender Minority Young Adults: Statistical Analysis Plan**

A mixed-methods approach will be used to understand feasibility, acceptability, and longitudinal effects of this single-arm clinical trial. Descriptive statistics will be used to summarize feasibility and acceptability measures from the full sample. These measures include recruitment rates, retention/attrition rates, session attendance, Client Satisfaction Questionnaire, and session evaluation form.

In addition, qualitative data from exit interviews will be analyzed using template analysis, a thematic analysis methodology that applies data reduction techniques for rapid turnaround, often used in intervention development and refinement research.

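### Does the SAP need a written analysis for the longitudinal effects it names as a goal?

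*SAP*

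**What the plan says.** The SAP opens with three goals, "feasibility, acceptability, and longitudinal effects of this single-arm clinical trial". Two methods follow. The quantitative one is limited in scope: "Descriptive statistics will be used to summarize feasibility and acceptability measures from the full sample". The measures listed for it are recruitment, retention or attrition, attendance, a satisfaction questionnaire and a session evaluation form. The other method is qualitative: "qualitative data from exit interviews will be analyzed using template analysis".

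The protocol has no quantitative analysis section. Its one analysis statement for this study, in section 7 (exit interview, item 4), is "Team will transcribe and analyze qualitative data".

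The protocol does schedule outcome data. Section 5 lists, at baseline, "primary outcomes (sexual risk behavior only, no testing" (item 1b), followed by secondary and exploratory outcomes. Item 3 repeats them later: "At post-intervention (2.5 months FU), participants will complete assessments related to" the same three groups, plus acceptability. During the group, item 2 adds weekly reports, described as "monitoring of sexual risk (condomless sex" and "monitoring of depression (PHQ-9) and anxiety symptoms (GAD-7". Table 1 sets these out by time point and labels sexual risk behaviors as primary. The SAP ranks no outcome.

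**The concern.** Read literally, one of three stated goals has no method, and the outcome that the protocol calls primary has no planned estimate. If nothing is written down, the analyst could choose after seeing the data which of 12 outcomes to report, on what scale, and whether to use the weekly series.

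The single-arm design adds to this. Section 2 of the protocol admits people who report recent condomless anal sex (criterion 6) and distress on the PHQ-9 and GAD-7 (criterion 7). The same domains are then followed as outcomes without a control group. Scores could fall through regression to the mean or natural recovery and be read as benefit. Sexual risk is also a primary outcome of the randomised pilot in Aim 3, so a misreading could carry forward.

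**Working it through.** **1. Count of outcomes (protocol, Table 1).**
- Primary: sexual risk behaviors = 1.
- Secondary: PHQ-9, GAD-7, Internalized Homophobia, DERS, Sexual Compulsivity, Safe Sex Self-Efficacy = 6.
- Exploratory: PCL-5, resilience, UCLA Loneliness, HIV knowledge, PrEP willingness = 5.
- Total 1 + 6 + 5 = 12. None of the five measures that the SAP lists is among them, so 0 of 12 has a stated analysis. The protocol's section numbers run from 5 to 7, which may be misnumbering. No quantitative analysis text appears in what is available.

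**2. What Aim 2 needs.** Specific Aims describes Aim 2 as an open pilot (n = 18) that gathers feedback and ends in a finalised intervention protocol. Recruitment, retention, attendance, satisfaction, session evaluation and interviews serve that purpose, and all have a method. The Aim 3 sample (40) and outcomes are already fixed in the same section, so no Aim 2 effect estimate feeds into them. The primary label matches Aim 3's pair of primary outcomes (HIV testing and sexual risk) with testing removed, and is probably carried over from there.

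**3. What an analyst would do unprompted.** Section 3, item 9 gives each participant one identifier across time points, so baseline and post-intervention records can be paired. With one arm and one post-intervention assessment, the natural report is both summaries, the change and the number of pairs. The plan gives no alpha, power, SD or dropout rate for Aim 2, so there is no figure of its own to reproduce. The precision of such a report, for a roughly continuous score, is:

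half-width in SD of change = t(0.975, n − 1)/√n

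| Complete pairs | Half-width |
|---|---|
| 18 (Specific Aims) | 0.497 |
| 16 (assumed) | 0.533 |
| 14 (assumed) | 0.577 |
| 12 (assumed) | 0.635 |

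Intervals this wide describe change and settle nothing about efficacy. The formula does not suit a yes/no or skewed-count measure of sexual risk.

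**4. Regression to the mean.** Section 3 places eligibility at the online form and the Zoom screen (items 5 and 6), and the baseline survey afterwards as a separate step (items 6b and 8). Table 1 schedules PHQ-9 and GAD-7 at that survey. Some of the fall due to selection may therefore occur between screening and baseline, outside the baseline-to-post change. How much is unknown. Natural recovery after baseline remains possible.

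**5. Recall overlap.** Suppose that sexual risk were recorded as any or none over the 6 months used for eligibility. Baseline would then be near 100% by design, and if 2.5 months ran from the baseline survey, (6 − 2.5)/6 = 58% of the post-intervention window would precede baseline. If it ran from group start, with baseline a month earlier (section 3 puts recruitment a month before the group), the overlap would be (6 − 3.5)/6 = 42%. The documents give neither the recall period nor the scale, so these figures show no defect.

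**The case for a change.** The best argument for a change is that the gap lies inside the SAP itself. It names longitudinal effects, confines descriptive statistics to other measures, and stops. Exit interviews take place once, at the end, and cannot stand in for paired measurements. The protocol also adapts the primary label to this study by excluding testing, so the label is not purely an Aim 3 leftover. A few lines of text would close the gap without extra data collection, and would limit selective reporting across 12 outcomes and three weekly series.

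All of that is accurate as a description, and the freedom to choose what to report is real. It falls short of requiring a change for three reasons. Nothing that is written leads to a wrong analysis. Neither document attaches an efficacy claim or a go/no-go decision to these outcomes. And the choice that remains is narrow, because a paired descriptive summary is the obvious use of the data. The same gap could be closed by removing two words from the SAP and relabelling a table row, which shows that it is one of wording. Prescribing 12 confidence intervals in 18 people could itself encourage the efficacy reading that everyone wants to avoid. The weekly reports are described as monitoring, although Table 1 does tick the during-intervention column for those three outcomes.

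**Conclusion.** The omission is real, and no change to the plan follows. Twelve Table 1 outcomes have no stated analysis, and the SAP and Table 1 do not agree on whether anything is primary. Aim 2's conclusions on feasibility, acceptability and refinement rest on measures that the SAP does cover, and analysts can fill the rest sensibly with baseline and post-intervention summaries and change. At best, continuous scores would carry a 95% half-width of about 0.50 SD of change (18 pairs), rising to 0.64 if only 12 pairs were complete, which is an assumed number.

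This rests on two assumptions: that the primary label is largely inherited from Aim 3, and that change in a single arm selected for distress and recent condomless sex is reported descriptively and not offered as evidence of efficacy. If Aim 2 results were later used to claim an effect, the missing specification would matter more.
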